11.6 Source Documents

Source data is all information, original records of clinical findings, observations, or other activities in a clinical trial necessary for the reconstruction and evaluation of the trial. Source data are contained in source documents Examples of these original documents, and data records include: hospital records, clinical and office charts, laboratory notes, memoranda, subjects' diaries or evaluation checklists, pharmacy dispensing records, recorded data from automated instruments, copies or transcriptions certified after verification as being accurate and complete, microfiches, photographic negatives, microfilm or magnetic media, x-rays, subject files, and records kept at the pharmacy, at the laboratories, and at medico-technical departments involved in the clinical trial.

11.7 Case Report Forms

The study case report form (CRF) is the primary data collection instrument for the study. All data requested on the CRF must be recorded. All missing data must be explained. If a space on

the CRF is left blank because the procedure was not done or the question was not asked, write "N/D". If the item is not applicable to the individual case, write "N/A".

11.8 Records Retention

Records relating to a specific research activity, including research records collected by investigators, must be maintained for at least three years after completion of the research (45 CFR 46.115(b); 21 CFR 56.115(b); 21 CFR 312.62). This minimum retention period applies whether or not any subjects were enrolled in the study. If the research is FDA regulated, records should be retained for at least two years after approval of the investigational agent by FDA; if it is not approved, records should be retained at least two years after the study is terminated and FDA is notified (note the additional requirement below for clinical research studies). Clinical records, including consent forms that document clinical intervention or clinical diagnostic procedure research-related procedures, must be retained in medical records by the institution for at least seven years, per CUMC and NYP policy which is based on state law.

12. STATISTICAL CONSIDERATIONS

This is a single arm, phase Ib study with 2 co-primary endpoints:

- Feasibility: The primary objective of this trial is to determine the feasibility of the OncoTreat platform in guiding therapy. The primary outcome is whether a subject begins therapy on Part 2. Previous attempts to match subjects based on DNA profiling have yielded enrollment rates of 3-5% [14, 78]. We hypothesize that we will validate OncoTreat matches for 50% of subjects and that at least 30% of enrolled subjects (60% of matches) will begin therapy on Part 2. With 30 enrolled patients on Part 1, we will have 80% power to detect a treatment rate of 30% on Part 2 compared to a historical treatment rate of 5% with alpha of 0.05. We will also assess the "match rate" the fraction of patients who match with at leaset one drug. With 30 enrolled subjects, we will have 97% power with alpha = 0.05 to detect a 50% match rate (15 of 30 subjects) compared to a (liberal) estimated match rate of 20% based on DNA profiling in PDA.
- Efficacy: The primary clinical efficacy endpoint is the **objective response rate (ORR)** for OncoTreat-prioritized drugs, which corresponds to the number of patients whose tumors demonstrate a 30% or greater reduction from baseline in the sum of the diameters of all target lesions amongst all evaluable patients, as assessed by standard-of-care CT scans. We target estimating the ORR and the corresponding 95% confidence interval.

Secondary endpoints will include: 1) **disease control rate (DCR) at 16 and 24 weeks**, which corresponds to the number of patients whose tumors demonstrate either an objective response or stable disease, defined as a no more than 20% increase from baseline in the sum of the diameters of all target lesions; 2) **median progression-free survival (mPFS)**, defined as the median duration prior to the development of disease progression or patient death; 3) **overall survival (OS)**, defined as time from first dose of OncoType-informed drug to death due to any cause; and 4) **safety and tolerability**, defined as the incidence of Grade 3/4 AEs in terms categorized and graded according to NCI CTCAE v4.0. We will estimate DCR, mPFS, and OS and their 95% confidence interval.

The phase III trial (NAPOLI-1) that resulted in the FDA-approval of nanoliposomal irinotecan and 5-fluorouracil in the second-line setting demonstrated a median overall survival of 6.1 months versus 4.2 months for 5-fluorouracil monotherapy (primary endpoint), mPFS of 3.1 months, and an ORR of 16% (compared to 1% in the 5-fluorouracil arm) [7]. Fifty-one (12%) patients had not had previous treatment for metastatic disease, 234 (56%) had received one previous line of metastatic treatment, and 132 (32%) had previously received two or more lines of metastatic treatment. The disease control rate was less than 20% and did not differ between treatment groups. Thus, based on historical controls, the ORR for treatment-resistant metastatic PDAC is expected to be no more than 16%.

Using the above mentioned rates, a sample size of n = 9 achieves at least a 80% power to detect a difference of 25% in ORR (30% vs 5%) using a one-sided binomial test with a target alpha of 0.1. To be conservative, we use the minimum number of patients (9) expected to be treated in this calculation. If at the end of the study the total number of objective responses is greater than or equal to 2, we will be able to reject the historical rate of 5% at the significance level of 0.05 with power of 69% and OncoTreat will have demonstrated a clear signal of clinically meaningful improvement in the primary endpoint for patients with advanced, previously-treated PDA. Assuming about 30% of enrolled patients will receive an OncoTreat-informed treatment, N = 30 subjects is an appropriate sample size for this prospective study.

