10. MEASUREMENT OF EFFECT

10.1 Antitumor Effect – Solid Tumors

For the purposes of this study, patients should be re-evaluated for response every 8 weeks. In addition to a baseline scan, confirmatory scans should also be obtained 8 weeks (not less than 4) weeks following initial documentation of objective response.

Response and progression will be evaluated in this study using the new international criteria proposed by the revised Response Evaluation Criteria in Solid Tumors (RECIST) guideline (version 1.1) [Eur J Ca 45:228-247, 2009]. Changes in the largest diameter (unidimensional measurement) of the tumor lesions and the shortest diameter in the case of malignant lymph nodes are used in the RECIST criteria.

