10.5.2 Evaluation of Non-Target Lesions

Complete Response (CR): Disappearance of all non-target lesions and normalization of tumor marker level. All lymph nodes must be non-pathological in size (< 10 mm short axis).

Note: If tumor markers are initially above the upper normal limit, they must normalize for a patient to be considered in complete clinical response.

Non-CR/Non-PD: Persistence of one or more non-target lesion(s) and/or maintenance of tumor marker level above the normal limits.

Progressive Disease (PD): Appearance of one or more new lesions and/or unequivocal progression of existing non-target lesions. Unequivocal progression should not normally trump target lesion status. It must be representative of overall disease status change, not a single lesion increase. Although a clear progression of "non-target" lesions only is exceptional, the opinion of the treating physician should prevail in such circumstances, and the progression status should be confirmed at a later time by the review panel (or Principal Investigator).

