10.5.3 Evaluation of Best Overall Response

The best overall response is the best response recorded from the start of the treatment until disease progression/recurrence (taking as reference for progressive disease the smallest measurements recorded since the treatment started). The patient's best response assignment will depend on the achievement of both measurement and confirmation criteria.

Target Lesions	Non-Target Lesions	New Lesions	Overall Response	Best Overall Response when Confirmation is Required*
CR	CR	No	CR	≥ 4 wks.
				Confirmation**
CR	Non-CR/Non-PD	No	PR	
CR	Not evaluated	No	PR	\geq 4 wks.
PR	Non-CR/Non-	No	PR	Confirmation**
	PD/not evaluated			
SD	Non-CR/Non-	No	SD	documented at least
	PD/not evaluated			once \geq 4 wks. from
				baseline**
PD	Any	Yes or	PD	
		No		
Any	PD***	Yes or	PD	no prior SD, PR or CR
		No		
Any	Any	Yes	PD	

Table 10Disease Assessment For Patients with Measurable Disease

* See RECIST 1.1 manuscript for further details on what is evidence of a new lesion.
 ** Only for non-randomized trials with response as primary endpoint.

*** In exceptional circumstances, unequivocal progression in non-target lesions may be accepted as disease progression.

Note: Patients with a global deterioration of health status requiring discontinuation of treatment without objective evidence of disease progression at that time should be reported as "symptomatic deterioration." Every effort should be made to document the objective progression even after discontinuation of treatment.

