10.7.1 Objective Response Rate (ORR)

ORR is defined as the proportion of the subjects in the analysis population who have a CR or PR. Responses are based on assessments per RECIST 1.1.

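### Section 12 describes the co-primary ORR by target-lesion shrinkage alone, which taken literally counts unconfirmed and mixed responses that Section 10.5.3 and Table 10 exclude; with a two-response success rule, one such subject can change the conclusion

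*Combined protocol and SAP*

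**What the plan says.** Section 12 (Efficacy) equates the ORR with "the number of patients whose tumors demonstrate a 30% or greater reduction from baseline in the sum of the diameters of all target lesions", counted "amongst all evaluable patients, as assessed by standard-of-care CT scans". That bullet sets no other condition for being a responder.

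Section 10 sets more conditions:

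- Section 10.5.3: "The patient's best response assignment will depend on the achievement of both measurement and confirmation criteria". Table 10 asks for confirmation at 4 weeks or more for CR and PR. Its footnote limits this: "Only for non-randomized trials with response as primary endpoint". A single-arm trial with ORR as a co-primary endpoint fits that description.
- Section 10.5.2 defines progression to include "Appearance of one or more new lesions and/or unequivocal progression of existing non-target lesions". Table 10 makes either of these an overall PD, whatever the target lesions do.
- Section 10.1 says that "confirmatory scans should also be obtained 8 weeks (not less than 4) weeks following initial documentation of objective response".
- Section 10.7.1: "ORR is defined as the proportion of the subjects in the analysis population who have a CR or PR". It cites RECIST 1.1 but says neither confirmed nor best overall response.

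Section 2.1.2 and the synopsis define the co-primary endpoint as ORR by RECIST v1.1, also without mentioning confirmation. The later part of Section 12 sizes the ORR test on 9 subjects (30% against 5%, one-sided binomial, target alpha 0.1) and declares a clear signal at 2 or more objective responses.

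**The concern.** An analyst who programs the endpoint from the statistical section would count as a responder anyone whose target sum falls by 30% at any scan. Two kinds of subject would then be counted although Table 10 does not count them: those whose shrinkage is not confirmed, and those with a new lesion or non-target progression at the same scan. The second kind would be a responder for ORR and a progression event for PFS on the same date. The confirmatory scans requested in Section 10.1 would play no part in the endpoint.

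The threshold is so low that a single reclassified subject can decide a co-primary result. The trial is open-label, so an unsettled rule could be settled after the responses are known.

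**Working it through.** **1. Which subjects differ.** Two constructed cases:

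- (a) Target sum −32% at week 8 with a new liver lesion. Section 12 read literally: responder. Table 10: PD.
- (b) Target sum −31% at week 8 and −10% at week 16. Section 12 read literally: responder. Section 10.5.3: PR not confirmed. The sum has gone from 69% to 90% of baseline, and 90/69 = 1.30, a 30% rise from the smallest sum. Under Section 10.5.1 that is PD if the rise is at least 5 mm, meaning a baseline sum of 5/0.21, about 24 mm, or more.

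The difference runs one way. A Table 10 PR based on target lesions needs a 30% fall. A target-lesion CR implies at least that much, even for nodes (15 mm or more down to under 10 mm is a fall of more than 5/15 = 33%). So the literal Section 12 count is never below the confirmed count.

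**2. The plan's own figure.** For 9 subjects and a rule of 2 or more:

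P(X ≥ 2) = 1 − (1 − p)^9 − 9p(1 − p)^8

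- p = 0.30: 1 − 0.04035 − 0.15565 = 0.804. The stated power of at least 80% reproduces.
- p = 0.05: 1 − 0.63025 − 0.29854 = 0.0712, inside the 0.1 target.

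(Section 12 also quotes a 0.05 level with 69% power for this rule. Its exact level is 0.071, so it does not meet 0.05. That is a separate matter and is not used here.)

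**3. What one subject does.**

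| Responders | ORR | Exact 95% CI | One-sided p against 5% | Rule met? |
|---|---|---|---|---|
| 2/9 | 22.2% | 2.8% to 60.0% | 0.071 | yes |
| 1/9 | 11.1% | 0.3% to 48.2% | 1 − 0.95^9 = 0.370 | no |

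**4. Sensitivity of the error rates.** Let c be the share of literal Section 12 responders who also meet the confirmed definition. The documents do not give c, so the range is an assumption. Two separate scenarios follow, not to be combined:

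- A: 5% is a confirmed rate, but Section 12 responses are counted. The counted rate is 0.05/c.
- B: 30% is a Section 12 rate, but confirmed responses are counted. The counted rate is 0.30 × c.

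| c | A: counted rate | A: type I error | B: counted rate | B: power |
|---|---|---|---|---|
| 1.0 | 5.0% | 7.1% | 30% | 80.4% |
| 0.9 | 5.6% | 8.6% | 27% | 74.5% |
| 0.8 | 6.3% | 10.5% | 24% | 67.5% |
| 0.7 | 7.1% | 13.1% | 21% | 59.3% |
| 0.6 | 8.3% | 16.9% | 18% | 50.1% |

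In scenario A the 0.1 target is exceeded once c falls to 0.8. If 5% and 30% are both confirmed rates and confirmed responses are counted, alpha 0.071 and power 0.804 stand unchanged.

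**The case against.** The strongest reply is that Section 12 is shorthand. A 30% fall is the RECIST threshold for PR. Section 2.1.2, the synopsis and Section 10.7.1 all tie the endpoint to RECIST 1.1. Section 12 restricts the count to evaluable patients, and Section 10.2, which defines evaluability for response, says that these patients are classified by the definitions that follow it. Those include Sections 10.5.2 and 10.5.3 and Table 10. Silence about confirmation is not a statement that confirmation is waived.

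Most of this stands. A reader might infer that the plan contains two rival ORR definitions of equal standing, with nothing to say which governs. The documents do not support that, because the cross-references favour Section 10.

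What remains is narrower. None of the endpoint definitions says that responses must be confirmed, and Table 10 has one column for overall response and another for best overall response, so a CR or PR in the sense of 10.7.1 could be taken from either. Section 12 also departs from Section 10 a second time: it measures stable disease against baseline, where Section 10.5.1 uses the smallest sum on study. The statistical section is where the success rule sits, and its wording is the one that would be programmed.

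A second objection also stands. The inflation in scenario A needs 5% to be a confirmed rate, which the documents do not say. If 5% already describes responses counted as in Section 12, the type I error stays at 7.1%.

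**Conclusion.** The point holds as a wording defect in a co-primary endpoint. Section 12, followed literally, counts responses that Section 10.5.3 and Table 10 exclude, and Section 10.7.1 does not close the gap. The firm consequence is that, with 2 or more responses needed in about 9 subjects, one unconfirmed or mixed response can turn a result that misses the rule (1/9, p = 0.370) into one that meets it (2/9, p = 0.071).

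A reader might go further and conclude that the trial's type I error is 8.6% to 16.9%. The documents do not support that as a finding. It rests on an assumed 10% to 40% of Section 12 responses failing the confirmed definition, on the 5% null being a confirmed rate, and on the analysis following Section 12 literally. The two counts may coincide in practice. The wording should be settled before any response is analysed.

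**What to change.** 1. In Section 12, define ORR as the proportion of subjects whose best overall response is confirmed CR or confirmed PR under Section 10.5.3 and Table 10. This takes in target, non-target and new lesions, with confirmation at least 4 weeks after first documentation.
2. Insert *confirmed* before CR or PR in Section 10.7.1.
3. Apply the two-response rule to confirmed responses, and report unconfirmed responses separately.
4. State that the 5% null and the 30% alternative are confirmed response rates, in which case alpha 0.071 and power 0.804 stand. If 30% is not a confirmed rate, restate the power.

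The cost is wording in two sections. No scans are added, because Section 10.1 already asks for confirmatory imaging and Section 9.1 already schedules scans every 8 weeks. The reported ORR may be lower. If 30% turns out to be an unconfirmed rate, power falls below the stated 80%, for example to 0.745 or 0.675 if 90% or 80% of responses are confirmed.

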This is a single arm, phase Ib study with 2 co-primary endpoints: 1. Feasibility Endpoint: We will determine the feasibility of the OncoTreat platform in guiding therapy. The primary feasibility endpoint is whether a subject begins treatment on Part 2 based on results generated from the OncoTreat analysis. Previous attempts to match subjects based on DNA profiling yielded enrollment rates of 3-5%. We hypothesize that we will validate OncoTreat matches for 50% of subjects and that at least 30% of enrolled subjects (60% of matches) will begin therapy. With 30 enrolled patients we will have 84% power to detect a treatment rate of 30% compared to a historical treatment rate of 5% with alpha of 0.05. We will assess the "match rate" – the fraction of patients who match with at least one drug. With 30 enrolled patients, we will have 90% power with alpha = 0.05 to detect a 50% match rate (15 of 30) subjects) compared to a (liberal) estimated match rate of 20% based on DNA profiling in pancreatic cancer. 2. Clinical Endpoint: The primary clinical efficacy endpoint is the objective response rate for OncoTreat-prioritized drugs according to RECIST v1.1. The phase III trial (NAPOLI-1) that resulted in the FDAapproval of nanoliposomal irinotecan and 5-fluorouracil in the second-Statistical line setting demonstrated a median OS of 6.1 months versus 4.2 months Methodology for 5-fluorouracil monotherapy (primary endpoint), mPFS of 3.1 months, and an ORR of 16% (compared to 1% in the 5-fluorouracil arm). Thus, based on historical controls, the ORR for treatment-resistant metastatic PDAC is expected to be no more than 16%. Using the above mentioned rates, a sample size of n = 9 achieves at least a 80% power to detect a difference of 25% in ORR (30% vs 5%) using a one-sided binomial test with a target alpha of 0.1. To be conservative, we use the minimum number of patients (9) expected to be treated in this calculation. If at the end of the study the total number of objective responses is greater than or equal to 2, we will be able to reject the historical rate of 5% at the significance level of 0.05 with power of 69% and OncoTreat will have demonstrated a clear signal of clinically meaningful improvement in the primary endpoint for patients with advanced, previously-treated PDA. Assuming about 30% of enrolled patients will receive an OncoTreat-informed treatment, N = 30subjects is an appropriate sample size for this prospective study. Secondary measures include DCR, PFS, and OS as well as safety and tolerability of OncoTreat-directed therapy. The pharmacokinetics of OncoTreat-prioritized drugs in PDA subjects will also be described.

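### Two or more responses can support activity above a 5% ORR, but not the clinically meaningful improvement the plan attaches to that result; the 5% null is not derived and the plan's own historical ceiling is 16%.

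*Combined protocol and SAP*

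**What the plan says.** Section 12 and the Statistical Methodology row of the synopsis carry the same argument for ORR. They cite the phase III second-line trial, with an ORR of 16% for the combination and 1% for 5-fluorouracil alone, and conclude: "Thus, based on historical controls, the ORR for treatment-resistant metastatic PDAC is expected to be no more than 16" percent.

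The power statement comes next: "Using the above mentioned rates, a sample size of n = 9 achieves at least a 80% power". The comparison is 30% against 5%, "using a one-sided binomial test with a target alpha of 0.1". Nine is described as the fewest patients expected to be treated: "To be conservative, we use the minimum number of patients (9) expected to be treated in this calculation".

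The success rule reads "If at the end of the study the total number of objective responses is greater than or equal to 2", in which case "we will be able to reject the historical rate of 5% at the significance level of 0.05 with power of 69" percent, and "OncoTreat will have demonstrated a clear signal of clinically meaningful improvement in the primary endpoint" for patients with advanced, previously treated disease.

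Section 12 also says that the ORR will be estimated with a 95% confidence interval.

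**The concern.** The power sentence claims to use the rates just given, but 5% is neither of them. No response rate of 5% appears earlier in the statistical text. The only earlier historical 5% there is the treatment rate for the feasibility endpoint, which is a different quantity. The plan still calls 5% the historical rate and gives no derivation.

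The larger problem is the step from test to conclusion. A one-sided test that rejects 5% says that the ORR is probably above 5%. It does not address rates between 5% and 16%, a range the plan itself leaves open for existing treatment. A clinically meaningful improvement for this population is a stronger statement, and the rule does not test it. A treatment whose true ORR lay anywhere in that range could be reported as a clear improvement on a co-primary endpoint.

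**Working it through.** **Inputs.** n = 9, null 5%, alternative 30%, one-sided target alpha 0.1, cut-off 2 responses, ceiling 16% (all Section 12). 15 subjects expected to progress to Part 2 (synopsis, Number of Subjects). The 10% rate is an illustrative midpoint that I chose; it is not in the plan.

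**Formula.** For X responses among n patients with true ORR p:

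P(X ≥ 2) = 1 − (1 − p)^n − n·p·(1 − p)^(n−1)

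**Step 1: reproduce the plan's figure.**
- p = 0.30, n = 9: 1 − 0.0404 − 0.1556 = 0.804. This matches the stated power of at least 80%.
- p = 0.05, n = 9: 1 − 0.6302 − 0.2985 = 0.0712. This is within the target alpha of 0.1.

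The cut-off of 2 therefore belongs to the alpha 0.1 design. The 0.05 level and 69% power that the plan also attaches to it are not its exact values (7.1% and 80.4%). A continuity-corrected normal approximation at one-sided 0.05 gives 68.8%, which may be where 69% comes from. That is a separate inconsistency.

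**Step 2: chance of meeting the rule at other true rates, n = 9.**
- p = 0.10: 1 − 0.3874 − 0.3874 = 0.225
- p = 0.16: 1 − 0.2082 − 0.3569 = 0.435

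**Step 3: more patients treated, cut-off still 2.** With n = 15 and p = 0.16: 1 − 0.0731 − 0.2090 = 0.718. At n = 15 and p = 0.05 the chance is 0.171, above the 0.1 target. Both figures are conditional: the plan presents the cut-off inside an n = 9 calculation and does not say whether it changes with more patients.

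**Step 4: what an observed 2 of 9 shows.** The point estimate is 2/9 = 22.2%. The exact (Clopper-Pearson) 95% interval is 2.8% to 60.0%, which contains both 16% and 5%.

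**Step 5: what it would take to show improvement over 16% with 9 patients.**

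| Criterion | Responses needed | Check | Power at ORR 30% |
|---|---|---|---|
| One-sided exact 5% test against 16% | 4 of 9 | P(X ≥ 4 at 16%) = 4.2%; P(X ≥ 3 at 16%) = 16.3% | 27.0% |
| Exact two-sided 95% interval excludes 16% | 5 of 9 | lower limit 21.2%; for 4 of 9 it is 13.7% | 9.9% |

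These are different rules. Neither has useful power with 9 patients.

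**The case against.** The strongest reply is that 16% is an upper bound and not the expected value. It comes from a two-drug regimen in a trial where 12% of patients had no previous treatment for metastatic disease and 56% had one line. This study gives single agents after one or two lines (Section 1.1), and Section 3.1 says there is no standard third-line regimen.

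Response rates elsewhere in the protocol, for the three named drugs, lie near 5%:
- Capecitabine alone in untreated patients: 3 of 42 = 7.1% (Section 3.6).
- Imatinib: no responses (Section 3.7).
- High-CRP subgroup of the ruxolitinib trial: 3.4% with capecitabine plus placebo, 6.5% with ruxolitinib added (Section 3.8).

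At 3.4% the rule is met with probability 1 − 0.7325 − 0.2320 = 0.0355; at 7.1% it is 0.131. Both are far below 43.5%.

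This part stands. A reader might infer that 43.5% is the design's false-positive rate, or that 5% is shown to be too low. The documents support neither. The error rate at the stated null is 7.1%, and 5% is unexplained, not refuted. A reader might also infer that the plan claims superiority over the 16% regimen. It does not say so; the rate it says it rejects is 5%.

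It is also fair that this is a phase Ib study gathering preliminary efficacy data (Section 4), that a confidence interval is planned, and that Section 10.11 hangs no stopping decision on the rule.

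What the reply does not rescue is the wording. The plan cites none of these single-agent data for its null, and it says that its rates are the ones just quoted. Patients may also start the study drug at first progression (Section 4.1), where the 16% regimen is the one approved option (Section 3.5). The planned interval would sit beside a claim that it does not support.

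**Conclusion.** The concern holds as a mismatch between rule and conclusion. Two responses among 9 patients reject 5% at an exact one-sided level of 7.1%, and that is all they show. The same result would occur 22.5% of the time at a true ORR of 10% and 43.5% of the time at 16%. These figures assume exactly 9 patients counted for response and exact binomial sampling with one common response probability. The 71.8% at 16% further assumes that 15 are treated and the cut-off stays at 2.

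The size should be read as a range over plausible historical rates, with 43.5% as its upper end at n = 9. The sample size and the choice of 5% are not shown to be wrong. The missing pieces are a reason for 5% and a conclusion limited to what rejecting it can support.

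**What to change.** In Section 12 and the synopsis:

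1. Replace the claim of clinically meaningful improvement with evidence of activity above an ORR of 5%, giving the exact level of 7.1% for 2 of 9.
2. Either justify 5% as the null from single-agent data, or state that it is a minimum-activity screen. Delete the phrase saying that the calculation uses the rates cited just before it.
3. State beside the rule its chance of success with 9 patients: 7.1% at ORR 5%, 22.5% at 10% and 43.5% at 16%. Say that these figures and the cut-off of 2 belong to 9 patients.
4. Report the exact 95% confidence interval for ORR against 16%, and state that 9 patients cannot credibly show improvement over 16%: 5 of 9 responses for the interval to exclude it (power 9.9% at ORR 30%), or 4 of 9 for a one-sided 5% test (power 27%).

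The cost is wording only, with no extra patients or assessments. The downside is real: the claim available after two responses becomes less favourable, and the plan would say openly that it cannot establish improvement over its own ceiling.

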	(CTCs) by comparing master regulators generated from
	CTCs to those obtained from tumor tissue in matched
	pre- and on-treatment samples with an OncoTreat-
	informed agent.
•	Identify associations between master regulator profiles
	and additional clinical, epidemiological, physiological,
	imaging, or molecular features of the subject or subject's
	tumor.
•	Identify potential biomarkers, beyond the master
	regulator signature, using additional genomic, RNA,
	protein, and imaging platforms that are predictive or

	prognostic of response to each OncoTreat-prioritized agent.
Number of Subjects	We will enroll 30 subjects in Part 1 (AAAR6703) of the study to obtain detailed predicted therapy options. We anticipate accrual over 15-18 months. We estimate that 15 subjects will progress to Part 2, requiring an additional 15-18 months to complete treatment and for follow-up.
Diagnosis and Main Inclusion Criteria	Locally advanced, unresectable or metastatic pancreatic cancer who progressed on one or two prior lines of chemotherapy, for whom a precision therapy was recommended in Part 1.
Duration of administration	Treatment will continue until progressive disease, unacceptable adverse events, intercurrent illness that prevents further administration of treatment, investigator's decision to withdraw the subject, subject withdrawal of consent, pregnancy of the subject, noncompliance with trial treatment or procedure requirements, or administrative reasons requiring cessation of treatment.
Reference therapy	Not applicable – single arm study.

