4.2 Number of Patients

Thirty subjects will be enrolled on Part 1 and, therefore, up to a maximum of 30 subjects will receive OncoTreat-prioritized agents on Part 2. No subjects will be replaced.

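### The ORR power calculation calls 9 treated patients a conservative minimum, but 9 is the expected number at the lowest hypothesised treatment rate; allowing for that, power is about 77% (72% with alpha held at 0.10), and the synopsis figure of 15 needs reconciling.

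*Combined protocol and SAP*

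**What the plan says.** Section 12 (Statistical Considerations), repeated under Statistical Methodology in the synopsis, tests an ORR of 30% against 5% with n = 9, "using a one-sided binomial test with a target alpha of 0.1", and claims power of at least 80%. The choice of nine is explained as follows: "To be conservative, we use the minimum number of patients (9) expected to be treated in this calculation". Success is two or more objective responses; no denominator is attached to that rule.

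The same paragraph closes the sizing argument with "Assuming about 30% of enrolled patients will receive an OncoTreat-informed treatment, N = 30 subjects is an appropriate sample size". The feasibility paragraph of Section 12 states the hypothesis as a 50% validated match rate, and that "at least 30% of enrolled subjects (60% of matches) will begin therapy on Part 2".

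Section 4.2 fixes Part 1 enrolment at 30, sets 30 as the ceiling for Part 2, and adds "No subjects will be replaced". It sets no floor. The synopsis, under Number of Subjects, says "We estimate that 15 subjects will progress to Part 2".

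**The concern.** The number treated is not set by design. It is the outcome of the feasibility co-primary endpoint, so it varies from one realisation of the trial to the next. Thirty times 30% is the centre of that distribution. Sizing a test at the centre is ordinary practice, but it gives no protection against a shortfall, so conservative minimum describes a safety margin that is not there.

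What is at stake is how a negative ORR result is read. Five treated out of 30 already gives a one-sided exact p-value of 0.016 against the 5% historical treatment rate. At a 30% treatment rate the chance of 5 to 8 treated is 4.6% + 8.3% + 12.2% + 15.0% = 40%. In those cases feasibility looks successful while the ORR test has only 47% to 74% power. A reader told that the calculation was conservative would give too much weight to a failure to reject.

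**Working it through.** **Inputs.** Enrolled 30, no replacement (Section 4.2). Treatment rate 30%, null ORR 5%, alternative ORR 30%, one-sided alpha target 0.10, rule of two or more responses (Section 12). Assumptions: subjects start treatment independently, response is independent of starting, and every treated subject is evaluable for response.

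**1. The plan's own figure.** With n = 9 and rejection at two or more responses:
- Power = 1 − 0.7^9 − 9 × 0.3 × 0.7^8 = 1 − 0.0404 − 0.1556 = 0.804.
- Alpha = 1 − 0.95^9 − 9 × 0.05 × 0.95^8 = 1 − 0.6302 − 0.2985 = 0.071.

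The claim of at least 80% at a target alpha of 0.10 reproduces, with almost no margin.

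**2. Where nine comes from.** 30 × 0.30 = 9; equivalently 30 × 0.50 matched = 15, and 15 × 0.60 = 9.

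**3. Chance of a shortfall.** With the number treated N ~ Binomial(30, 0.30), P(N ≤ 8) = 0.432. The 5th to 95th percentile range is 5 to 13.

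**4. Power and alpha at each N in that range.**

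| N | P(N) | ≥2: alpha | ≥2: power | Cutoff for alpha ≤ 0.10 | Its alpha | Its power |
|---|---|---|---|---|---|---|
| 5 | 4.6% | 0.023 | 47% | ≥2 | 0.023 | 47% |
| 6 | 8.3% | 0.033 | 58% | ≥2 | 0.033 | 58% |
| 7 | 12.2% | 0.044 | 67% | ≥2 | 0.044 | 67% |
| 8 | 15.0% | 0.057 | 74% | ≥2 | 0.057 | 74% |
| 9 | 15.7% | 0.071 | 80% | ≥2 | 0.071 | 80% |
| 10 | 14.2% | 0.086 | 85% | ≥2 | 0.086 | 85% |
| 11 | 11.0% | 0.102 | 89% | ≥3 | 0.015 | 69% |
| 12 | 7.5% | 0.118 | 91% | ≥3 | 0.020 | 75% |
| 13 | 4.4% | 0.135 | 94% | ≥3 | 0.025 | 80% (79.8%) |

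**5. Overall power.** Each enrolled subject becomes a treated responder with probability 0.30 × 0.30 = 0.09, so responders ~ Binomial(30, 0.09):
- P(≥2) = 1 − 0.91^30 − 30 × 0.09 × 0.91^29 = 1 − 0.0591 − 0.1752 = 0.766.
- Average power given N < 9 is 63.1%.
- With the cutoff reset at each N so that exact alpha stays at or below 0.10, the sum of P(N) × power(N) is 0.722.

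**6. Sensitivity to the treatment rate.**

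| Treatment rate | P(N < 9) | Overall power, ≥2 rule | Overall power, alpha ≤ 0.10 at each N |
|---|---|---|---|
| 25% | 67% | 67% | 65% |
| 30% | 43% | 77% | 72% |
| 35% | 22% | 84% | 76% |
| 40% | 9% | 89% | 79% |
| 50% | 0.8% | 95% | 86% |

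**7. The synopsis figure.** Fifteen equals the expected matches (50% of 30). If it meant treated, the treatment rate would be 50%, not 30%. With exactly 15 treated, the ≥2 rule has alpha 0.171; holding 0.10 needs ≥3 (alpha 0.036, power 87%).

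**The case against.** The power sentence is conditional: it says what nine patients achieve, and that is right. A reader might infer that the 80% is an arithmetic mistake; the documents do not support that. Averaging over N answers a different question, and the drop is under four points (80.4% to 76.6%).

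The word minimum also has some basis. The feasibility hypothesis is a rate of 30% or more, so nine is the smallest expected count under that hypothesis. On that reading, 43% is the largest chance of a shortfall and 77% the smallest overall power for the ≥2 rule. Section 3.4 also reports a preliminary 85% match rate, well above the planned 50%, although the 50% refers to validated matches. This stands in part. A floor on the rate is still not a floor on the count, and the sizing paragraph itself assumes a rate of about 30%, not a lower bound.

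Averaged over N at a 30% treatment rate, the ≥2 rule has a type I error of 7.4%, so exceeding 0.10 from N = 11 is a conditional failing, not an overall one. That is why both 77% and 72% are given.

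A reader might also infer that the synopsis is wrong and should say nine. The documents do not establish that. Under Section 4.1, consent to Part 2 and a required biopsy come before dosing, so 15 entering and nine dosed can coexist. The synopsis sentence goes on to mention time for treatment, which leaves the meaning open. If 15 were the number treated, nine would indeed be conservative.

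Finally, Section 12 also aims to estimate the ORR with a 95% confidence interval. Reporting that interval would limit over-reading of a negative test.

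**Conclusion.** The concern holds as a matter of labelling and unstated uncertainty. Nine is the expected number treated at the lowest hypothesised rate, not a guaranteed or conservative minimum. The 80% is valid conditional on n = 9. At a 30% treatment rate the chance of fewer than nine is 43%, and overall power is about 77% with the fixed ≥2 rule or about 72% with one-sided alpha held at or below 0.10 at each N.

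These figures rest on independence between subjects, independence of response and starting treatment, and full evaluability. Section 10.2 allows the response-evaluable set to be smaller than the treated set, which would lower power further. The documents give no rate. Purely as an illustration, if 10% or 20% of treated subjects were not evaluable, responders would follow Binomial(30, 0.081) or Binomial(30, 0.072), and power would be 71% or 65%.

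The 15 in the synopsis is an ambiguity to resolve, not a proven error. The point should be fixed; it does not invalidate the sample size.

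**What to change.** In Section 12 and the matching synopsis text:

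- Delete the claim that nine is a conservative minimum. Call nine the number expected to be treated at a 30% treatment rate, and say that the 80% power is conditional on n = 9.
- Attach a denominator to the response rule. Tabulate power and exact alpha for 5 to 13 evaluable treated subjects, as in step 4 above, showing that three or more responses are needed from 11 to keep alpha at or below 0.10. Choose between the fixed and the reset cutoff in advance.
- State overall power of about 77% (72% with alpha held at each N), with the 25% and 35% treatment-rate values as sensitivity.
- In the synopsis, say whether the 15 subjects are matched, consented or treated, and reconcile that with the nine expected to begin therapy.
- Do not write a power based on the assumed 10–20% non-evaluable rate into the protocol.

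The next sentence of Section 12, which gives a 0.05 level and 69% power for two or more responses, does not reproduce at n = 9 (0.071 and 80.4%). It should be corrected in the same edit so that one rule does not carry conflicting figures.

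The cost is a few sentences and a small table. No extra patients or procedures are needed; the stated power becomes slightly less favourable.
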